Appendix 2: Study Specific Definitions38

LIST OF ABBREVIATIONS AND TERMS

Abbreviation	Definition
ALT	Alanine aminotransferase
AST	Aspartate aminotransferase
BPI-SF	Brief Pain Inventory Short Form
CT	Computed tomography
CTCAE	Common Terminology Criteria for Adverse Events
DMC	Data Monitoring Committee
ECOG	Eastern Cooperative Oncology Group
EORTC	European Organization for Research and Treatment of Cancer
EQ-5D-5L	European Quality of Life 5 Dimensions-5 Levels health questionnaire
FACT-P	Functional Assessment of Cancer Therapy-Prostate
ICR	Independent Central Radiology review
ITT	Intent-to-treat
LOCF	Last observation carried forward
MedDRA	Medical Dictionary for Regulatory Activities
MFS	Metastasis-free survival
MRI	Magnetic resonance imaging
NCI	National Cancer Institute
OS	Overall survival
PSA	Prostate-specific antigen
PT	Preferred term
QLQ-PR25	Quality of Life Questionnaire-Prostate 25 module
SAP	Statistical analysis plan
SOC	System organ class
TEAE	Treatment-emergent adverse event

1. INTRODUCTION

This statistical analysis plan (SAP) contains definitions of analysis populations and endpoints, outlines the timing of statistical analyses, and provides a comprehensive description of statistical analyses to be implemented to assess the clinical efficacy and safety of Protocol MDV3100-14 (C3431005): A Multinational, Phase 3, Randomized, Double-Blind, Placebo-Controlled, Efficacy and Safety Study of Enzalutamide in Patients with Nonmetastatic Castration-Resistant Prostate Cancer. This SAP is based on protocol version 5.0 dated 26 January 2018.

2. STUDY OVERVIEW

Protocol MDV3100-14 is a multinational, Phase 3, randomized, double-blind, placebo-controlled efficacy and safety study in patients with nonmetastatic castration-resistant prostate cancer. The primary objective is to determine the efficacy of enzalutamide (formerly MDV3100) (160 mg/day by mouth) compared with placebo as assessed by metastasis-free survival (MFS). Patients will maintain androgen deprivation during the study, either using a gonadotropin-releasing hormone (GnRH) agonist/antagonist or will have a history of bilateral orchiectomy.

A total of 1440 patients will be centrally randomized in a 2:1 ratio to enzalutamide or placebo treatment within each stratum of prostate-specific antigen (PSA) doubling time (< 6 months vs. ≥ 6 months) and prior or current use of bone targeting agents (yes vs. no).

PSA doubling time will be calculated by the sponsor, using the method of Pound et al, 1999.¹ A linear regression model will be used with log-transformed PSA values as the response and the duration of time from the first reference PSA value as the explanatory variable. The slope from the fitted regression line will be used to calculate PSA doubling time in months as follows:

$$\text{PSA Doubling Time (months)} = \frac{\text{LN}(2)*12}{(365.25*\text{Slope of Log (PSA)})}$$

The study consists of screening, double-blind treatment, safety follow-up, and long-term follow-up periods. Radiographic assessments will be performed as described in Appendix 1 approximately every 16 weeks. Patients will continue study drug until radiographic progression. Radiographic progression will be confirmed by independent central radiology review before radiographic imaging stops.

In addition to imaging, the following assessments of prostate cancer status will be made during the study: survival status, PSA values, use of new antineoplastic therapy, pain intensity and interference using the Brief Pain Inventory Short Form (BPI-SF), and quality of life as assessed by the Functional Assessment of Cancer Therapy-Prostate (FACT-P) questionnaire, European Quality of Life-5 Dimensions-5 Levels health questionnaire (EQ-5D-5L) and the European Organization for Research and Treatment of Cancer (EORTC) Quality of Life Questionnaire-Prostate 25 (QLQ-PR25) module.

Safety will be assessed by monitoring adverse events, clinical laboratory tests, physical examinations, and vital signs during the treatment period through 30 days after the last dose of study drug or initiation of a new antineoplastic treatment, whichever occurs first. An independent Data Monitoring Committee (DMC) will periodically monitor the safety data.

During long-term follow-up, patients will be monitored for survival status, new antineoplastic therapies for prostate cancer, opiate medications, skeletal-related events, and interventions due to locoregional metastasis (eg, radiation, transurethral resection of the prostate, nephrostomy tube placement).

As the study met the primary efficacy endpoint of metastasis-free survival and the established safety profile of enzalutamide was confirmed based on the data cutoff on 28 June 2017, all patients were unblinded. Eligible patients from the placebo group were offered enzalutamide at the discretion of the investigator. For patients who had not progressed radiographically, scans (CT (computed tomography)/MRI (magnetic resonance imaging) and bone scan) were to be performed per investigator discretion until patient has progressed radiographically. Continuation of treatment on the open-label period after radiographic progression were at the discretion of the investigator. Patients who did not participate in the open-label period or withdrew consent for further treatment would continue long-term follow-up assessments per protocol. Treatment with open-labeled enzalutamide were to be stopped upon disease progression when in the opinion of the Investigator, there was no added clinical benefit to continue treatment with enzalutamide.

Long-term follow-up data (including survival status, new antineoplastic therapies for prostate cancer, skeletal-related events, and interventions due to locoregional progression) were to be collected every 16 weeks.

3. STUDY OBJECTIVES

The primary study objective is to determine the efficacy of enzalutamide compared with placebo as assessed by MFS.

The secondary objectives are as follows:

- To evaluate the benefit of enzalutamide compared with placebo as measured by the following:
 - Time to PSA progression;
 - Time to first use of new antineoplastic therapy;
 - Overall Survival (OS);
 - Time to pain progression;
 - Time to first use of cytotoxic chemotherapy;
 - Chemotherapy-free disease-specific survival;

- Chemotherapy-free survival;
 - PSA response rates;
 - Quality of life as assessed by the Functional Assessment of Cancer Therapy-Prostate (FACT-P) questionnaire, European Quality of Life-5 Dimensions-5 Levels (EQ-5D-5L) health questionnaire and Quality of Life Questionnaire-Prostate 25 (QLQ-PR25) module.
- To evaluate safety.

No exploratory objectives are planned; exploratory analyses will be performed as deemed necessary to assess the benefit-risk profile of enzalutamide.

4. STUDY ENDPOINTS

4.1. Primary Endpoint

The study has a single primary efficacy endpoint of MFS assessed by blinded Independent Central Radiology Review (ICR).

4.2. Secondary Endpoints

Secondary endpoints are as follows:

- Efficacy

Key secondary endpoints:

- Time to PSA progression;
- Time to first use of new antineoplastic therapy;
- Overall Survival;

Additional secondary endpoints:

- Time to pain progression;
- Time to first use of cytotoxic chemotherapy;
- Chemotherapy-free disease-specific survival;
- Chemotherapy-free survival;
- PSA response;
- Quality of Life as assessed by the FACT-P questionnaire, EQ-5D-5L health questionnaire, and QLQ-PR25 module.

- Safety.

4.3. Exploratory Efficacy Endpoints

There is no predefined exploratory endpoint.

5. SAMPLE SIZE CONSIDERATIONS

The following assumptions are used in determining the sample size calculation for the MFS endpoint:

- 2:1 enzalutamide to placebo treatment allocation;
- An increasing nonuniform accrual of 0.25 patients per month per site with maximum accrual of 63 patients per month;
- For MFS a target hazard ratio of 0.72 at a 2-sided significance level of 0.05 with 90% power. Under an exponential model assumption, the target difference in Kaplan-Meier estimated median is 9 months (24 months versus 33 months). The median MFS of 24 months for the placebo group is based on published data.²

A total of 440 events provide 90% power to detect a target hazard ratio of 0.72 based on a 2-sided log-rank test and the overall significance level of 0.05. A sample size of approximately 1305 patients (870 enzalutamide and 435 placebo) will achieve 440 events. Approximately 10% of patients enrolled are expected to be lost to follow-up, will be found to have metastatic disease at study entry, or will have events censored due to required analytical methods, so approximately 1440 patients (960 enzalutamide and 480 placebo) will be enrolled. The time from date of first randomization until 440 MFS events are observed is estimated to be approximately 43 months.

Approximately 500 PSA progression events are expected at the time of the single MFS analysis. Based on a hazard ratio assumption of 0.60, this endpoint will have >95% power at a 2-sided significance level of 0.02 (see [Section 9.7.1](#) for details on multiplicity adjustments on key secondary endpoints).

Approximately 360 new antineoplastic therapy events are expected at the time of the single MFS analysis. This endpoint will have 80% power to detect a hazard ratio of 0.70 at a 2-sided significance level of 0.02 (see [Section 9.7.1](#) for details on multiplicity adjustments on key secondary endpoints).

The study is also powered for OS. Specifically, 590 death events will be required to have 85% power to detect a hazard ratio of 0.77 at a 2-sided significance level of 0.05. Under an exponential model assumption, the target difference in Kaplan-Meier estimated medians is 13.7 months (46 months vs. 59.7 months). If either time to PSA progression or time to new antineoplastic therapy endpoint fails to show significance, OS will be tested at a 2-sided significance level of 0.03. Under this scenario, 590 death events will provide ~79% power to detect a hazard ratio of 0.77 (see [Section 9.7.1](#) for details on multiplicity adjustments on key secondary endpoints).

The sample size and power calculations were performed using the software package East 5.4 (Cytel Inc., Cambridge, MA).

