10.6. Determination of Sample Size

The following assumptions were used in determining the sample size for the MFS endpoint:

- 2:1 enzalutamide to placebo treatment allocation;
- Target hazard ratio of 0.72 at the 5% significance level with 90% power. The targeted difference in Kaplan-Meier estimated median is 9 months (24 months vs 33 months). The median MFS of 24 months for the placebo arm is based on published data from a similar clinical trial.²

A minimum of 440 MFS events provides 90% power to detect a target hazard ratio of 0.72 based on a 2-sided log-rank test at an overall significance level of 0.05. A sample size of approximately 1305 patients will achieve 440 events within approximately 43 months. It is assumed that a number of patients will be lost to follow-up, will be found to have metastatic disease at enrollment, or will have events censored due to required analytical methods. To account for this anticipated loss in contribution of events to the primary and

secondary endpoint analyses, an additional 135 patients (approximately 10% of 1305) will be enrolled to achieve a final sample size of 1440 patients (960 enzalutamide and 480 placebo).

The study is also powered for overall survival. Specifically, 590 death events will be required to provide 85% power to detect a target hazard ratio of 0.77 with a target difference in Kaplan-Meier estimated median of 13.7 months (46 months for placebo vs 59.7 months for enzalutamide) at the 5% significance level. The power analysis for the remaining key secondary endpoints will be discussed in the statistical analysis plan.

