Schematic - Open Label Treatment Period:

Inclusion Criteria:

The inclusion criteria apply to patients receiving enzalutamide or placebo during double-blind treatment. Eligible patients must meet all inclusion criteria.

1. Received randomized double-blind treatment in PROSPER;
2. Open-label day 1 visit is within 16 weeks after this amendment is approved and becomes effective at the study site;
3. Is willing to maintain androgen deprivation therapy with a gonadotropin-releasing hormone (GnRH) agonist/antagonist or has had a bilateral orchiectomy;
4. Is able to swallow enzalutamide capsules whole and to comply with study requirements throughout the study;
5. Throughout the study, a male patient and his female partner of childbearing potential must use 2 acceptable methods of birth control (1 of which must include a condom as a barrier method of contraception) starting at screening and continuing through 3 months after the final study drug administration or per local guidelines where these require additional description of contraceptive methods. Two acceptable methods of birth control thus include the following:

- Condom (barrier method);

AND

- One of the following is required:
 - Established and ongoing use of oral, injected, or implanted hormonal method by the female partner;
 - Placement of an intrauterine device or intrauterine system by the female partner;
 - Additional barrier method: Occlusive cap (diaphragm or cervical/vault caps) with spermicidal foam/gel/film/cream/suppository by the female partner;
 - Tubal ligation in the female partner;
 - Vasectomy or other procedure resulting in infertility (eg, bilateral orchiectomy), for > 6 months.
6. Male patient agrees to use a condom if having sex with a pregnant woman throughout the study;
 7. Agrees to avoid sperm donation while taking enzalutamide.

Exclusion Criteria:

The exclusion criteria apply only to patients starting new treatment with enzalutamide after receiving placebo as randomized treatment. Each patient must NOT meet any of the following criteria:

1. Has taken commercially available enzalutamide (Xtandi).
2. Patients who progressed radiographically on double-blind portion of the trial and stopped treatment with investigational drug due to any reason. Note that patients who progressed radiographically on double-blind portion of the trial and continued treatment per protocol are allowed to participate in the open-label period.

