3. Patients who started any other prostate cancer-related treatment after unblinding.
4. Has any clinically significant cardiovascular, dermatologic, endocrine, gastrointestinal, hematologic, hepatic, infectious, metabolic, neurologic, psychological, pulmonary, or renal disorder or any other condition, including excessive alcohol or drug abuse, or secondary malignancy, that may interfere with study participation in the opinion of the investigator or medical monitor;
5. Has current or previously treated brain metastasis or active leptomeningeal disease;
6. Has a history of seizure or a condition that may increase the risk of seizure;
7. Has any of the following: total bilirubin ≥ 1.5 -times the upper limit of normal (ULN) (except patients with a diagnosis of Gilbert's disease), ALT ≥ 2.5 -times ULN at screening, AST ≥ 2.5 -times ULN at screening. For patients with documented liver metastases, ALT and AST exclusion is >5 -times ULN; Absolute neutrophil count $< 1000/\mu\text{L}$, platelet count $< 100,000/\mu\text{L}$, or hemoglobin $< 10 \text{ g/dL}$ (6.2 mmol/L) at screening. NOTE: may not have received growth factors or blood transfusions within 7 days before obtaining the hematology values at screening. Albumin $< 3.0 \text{ g/dL}$ (30 g/L) at screening.
8. Has creatinine $>2 \text{ mg/dL}$ (177 $\mu\text{mol/L}$) at screening.

Enzalutamide Administration, Storage, and Accountability:

All patients will self-administer four 40-mg soft gelatin enzalutamide capsules (160 mg/day) by mouth once daily with or without food, unless they were receiving a reduced dose during double-blind treatment (treatment will continue at the reduced dose). Patients should return all study drug bottles, including unused study drug to the site at each visit.

Enzalutamide should be handled and stored safely and properly in accordance with the study drug label. Study site personnel must make all reasonable efforts to obtain all bottles and unused study drug from patients who do not routinely return the bottles at study site visits. Please refer to IP Manual.

Duration of Treatment and Criteria for Discontinuation:

Open-label enzalutamide administration may continue as long as the investigator considers treatment to be beneficial or until any intolerable adverse event develops.

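### Does offering enzalutamide to placebo patients undermine the overall survival power stated in SAP 5?

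*SAP*

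**What the plan says.** SAP 5 gives the OS design calculation twice. At the full level, "590 death events will be required to have 85% power to detect a hazard ratio of 0.77 at a 2-sided significance level of 0.05", with exponential medians of 46 and 59.7 months. If time to PSA progression or time to first new antineoplastic therapy fails, OS is tested at 0.03: "Under this scenario, 590 death events will provide ~79% power to detect a hazard ratio of 0.77". Protocol 10.6 has the first statement in nearly the same words ("590 death events will be required to provide 85% power to detect a target hazard ratio of 0.77").

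The rest of the SAP describes a trial that has moved on. SAP 1 says "This SAP is based on protocol version 5.0 dated 26 January 2018", the version with the open-label supplement. SAP 2 records that all patients were unblinded after the 28 June 2017 data cutoff and that "Eligible patients from the placebo group were offered enzalutamide at the discretion of the investigator".

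The exclusion criteria in Protocol Supplement 1 restrict who may switch. They bar "Patients who progressed radiographically on double-blind portion of the trial and stopped treatment with investigational drug due to any reason" and "Patients who started any other prostate cancer-related treatment after unblinding", but note that "patients who progressed radiographically on double-blind portion of the trial and continued treatment per protocol are allowed to participate in the open-label period".

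The Statistical Methods part of Supplement 1 keeps the primary OS analysis as ITT, says that it does not adjust for crossover, and names commercial enzalutamide and other commercial treatments as a further confounder. SAP 9.7.3 plans a rank-preserving structural failure time model as a sensitivity analysis at the final OS analysis, with inverse probability weighting as optional.

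**The concern.** Exponential medians of 46 and 59.7 months imply a constant hazard ratio (46/59.7 = 0.7705). That model has no term for placebo patients who start the active drug partway through. Three OS analyses, at about 285, 440 and 596 deaths, come after the MFS analysis, so many of the deaths they count could follow the switch. The structural failure time model addresses the estimate of effect; it does not give the primary log-rank test back its power. A non-significant ITT result could then be read against 85% power that the trial no longer had.

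A smaller point adds to the doubt. SAP 8 and 9.7 and Protocol 10.3 expect about 135 deaths at the MFS analysis without saying how that number arose. The medians in SAP 5 point to many more.

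**Working it through.** **Inputs.** From SAP 5: 590 deaths, hazard ratio (HR) 0.77, 2:1 allocation (p = 2/3), two-sided levels 0.05 and 0.03. From SAP Table 4: looks at 135, 285, 440 and 596 deaths with their significance levels.

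**Step 1: reproduce the plan's figures.** Schoenfeld's formula for the number of deaths is

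d = (z₁₋α/₂ + z_power)² / [p(1−p)(ln HR)²] = (1.960 + 1.036)² / [0.2222 × 0.0683] ≈ 592, against 590 stated.

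Power with 590 deaths is Φ(√(590 × 2/9) × |ln HR| − z₁₋α/₂):

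- at 0.05: Φ(11.450 × 0.2614 − 1.960) = Φ(1.033) = 84.9%
- at 0.03: Φ(11.450 × 0.2614 − 2.170) = Φ(0.823) = 79.5%

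Over the four looks at the Table 4 levels, multivariate normal integration gives 84.6% and 78.9%, with overall type I error of 0.0504 and 0.0297. Both stated figures hold.

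**Step 2: power by the average HR the ITT test faces** (590 deaths, same formula).

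| Average ITT HR | Power at 0.05 | Power at 0.03 |
|---|---|---|
| 0.77 | 84.9% | 79.5% |
| 0.78 | 81.2% | 75.0% |
| 0.80 | 72.4% | 65.0% |
| 0.82 | 62.3% | 54.1% |
| 0.85 | 46.1% | 37.9% |

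**Step 3: what crossover could do.** Uptake c and benefit r are assumptions, because the documents give neither. Suppose switching opens at 135 deaths to all living placebo patients. This is pessimistic on eligibility, since Supplement 1 excludes some of them. After the switch the HR is 0.77/(1 − c + c × 0.77^r), with r = 1 for full and r = 0.5 for half benefit. The log hazard ratios are averaged with weights 135/590 = 0.229 and 0.771.

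For c = 0.20 and r = 1: 0.77/0.954 = 0.807, and exp(0.229 × ln 0.77 + 0.771 × ln 0.807) = 0.798.

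| Uptake | Average HR, full benefit | Power at 0.05 / 0.03 | Average HR, half benefit | Power at 0.05 / 0.03 |
|---|---|---|---|---|
| 10% | 0.784 | 79.6% / 73.1% | 0.777 | 82.2% / 76.2% |
| 20% | 0.798 | 73.1% / 65.8% | 0.785 | 79.2% / 72.7% |
| 30% | 0.814 | 65.6% / 57.6% | 0.793 | 75.9% / 68.9% |
| 50% | 0.846 | 48.2% / 39.9% | 0.808 | 68.2% / 60.4% |

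A log-rank simulation (2,000 trials per scenario, assumed accrual ramp to 63 per month) agrees: with full benefit, power at 0.05 is 86.7% with no switching and 74.5% with 20% uptake.

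The loss is smaller if only placebo patients alive and free of an MFS event may switch, 7.0 to 10.7 months after the data cutoff, under SAP 5's medians. Power at 0.05 with full benefit is then 81–82%, 76–79% and 71–76% for 20%, 40% and 60% uptake. That window is itself an assumption: the cutoff to the date of protocol version 5, plus 16 weeks.

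**Step 4: is 0.77 necessarily an undiluted value?** Take an undiluted HR of 0.74 with 20% uptake and full benefit. The post-switch HR is 0.74/(0.8 + 0.2 × 0.74) = 0.74/0.948 = 0.781. The average is exp(0.229 × ln 0.74 + 0.771 × ln 0.781) ≈ 0.771, with power Φ(11.450 × 0.2599 − 1.960) = 84.5%. The stated power can therefore hold with crossover, if the drug's own effect is somewhat stronger than 0.77.

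**Step 5: the 135 deaths.** Under constant hazards the ratio of the death hazard to the MFS hazard is 24/46 = 0.522 on placebo and 33/59.7 = 0.553 on enzalutamide. Patients still free of an MFS event would therefore contribute at least 0.522 × 440 ≈ 230 deaths. Adding deaths after an MFS event gives about 266 under an assumed accrual ramp over 34 months to 63 per month. So 135 does not follow from these medians. It also drives nothing: the first OS look is tied to the MFS analysis and tested at a fixed 0.001, and the later levels are recalculated from actual deaths.

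**The case for a change.** The strongest case for a change is that the SAP postdates the decision to offer crossover and still prints 85% without qualification. Supplement 1 acknowledges that crossover confounds the OS comparison, but nothing says what it does to power. A caveat written before the remaining looks is more credible than one offered after a disappointing result, and it would cost one sentence and a small table.

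Much of this is true. SAP 5 is silent on crossover, beneficial switching would lower the power of the primary test, and the sensitivity analysis does not repair that. Three things weigh against it.

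- SAP 5 states power for an HR of 0.77, which is the usual form of such a statement. Whether that target allowed for later therapy is not recorded. The same section expects about 360 new antineoplastic therapy events by the MFS analysis, and Protocol 1.4 notes that the label already covers all metastatic disease. Writing that the power assumes no crossover would give the sponsor a design assumption that the documents do not contain.
- A reader of a negative ITT result is already warned. Supplement 1 names both crossover and commercial enzalutamide, and SAP 9.7.3 commits to an adjusted analysis.
- A table would rest wholly on assumed uptake, benefit and switch time. The scenarios in the working that differ only in these run from about 82% down to 48% at 0.05, so they illustrate a direction without yielding a corrected figure.

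**Conclusion.** No change to the plan follows. The stated power is arithmetically right for an average ITT HR of 0.77: 84.9% and 79.5% in a fixed design, and 84.6% and 78.9% over the four looks. If that target does not already allow for crossover, beneficial switching would lower the power by an amount the documents cannot fix; an average HR of 0.80, for instance, would give 72% at 0.05 and 65% at 0.03.

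The ITT test stays valid. If enzalutamide had no effect on survival, switching to it would have none either, so type I error is not inflated. The 596 deaths, the boundaries and the sample size would all stand with or without a caveat.

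The unexplained 135 deaths, against about 266 from the stated medians, is a gap in documentation for a look whose level and timing do not depend on it. A sentence in SAP 5 pointing to Supplement 1 would do no harm, but no analysis or conclusion depends on it. An analyst reporting a non-significant OS result would in any case discuss crossover from the text already in Supplement 1 and SAP 9.7.3.
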